#### 4.6.1. Risk Assessment

Potential Risk of Clinical Significance	Summary of Data/Rationale for Risk	Mitigation Strategy
Pregnancy & Lactation	
Fetal malformations were seen after IV dosing to pregnant Dutch belted rabbits with a NOAEL that is expected to exceed the highest expected human exposure by 13 and 214 fold cover compared to the predicted AUC (220 ng.hr/mL) and Cmax (167 ng/ml) respectively at the NOAEL.
 
In a subsequent study in the New Zealand White rabbits, neither cardiovascular nor skeletal abnormalities were detected by any route and dose at maternal plasma exposures similar to or higher than exposures achieved in Dutch Belted rabbit. Based on these new fetal and TK data, the abnormalities in the Dutch Belted rabbit study were unlikely to be test article-related because no fetal abnormalities were detected in the New Zealand White rabbit with a similar <math>C_{max}</math> (bolus route compared) or at a 4.5-fold higher AUC (bolus vs 24-hr continuous infusion compared). The higher number of specific cardiovascular and skeletal abnormalities observed in the Dutch Belted rabbit Embryofoetal Development (EFD) study is likely related to the known higher spontaneous background incidence of these findings in Dutch Belted relative to New Zealand White fetal rabbits based on Test Facility
	
Women who are pregnant, lactating or are planning on becoming pregnant during the study are not eligible to participate.
 
Female subjects of reproductive potential will undergo regular pregnancy testing (at screening, Day 1, Day 14, and at follow-up) and treatment will be stopped immediately if a subject is found to be pregnant during the study, see Section 7.1 for exact timings. Subjects will also be required to be using an appropriate contraceptive (failure rate <1%) prior to the start and during the study as outlined in the protocol Section 5.1, Inclusion criteria. Females of reproductive potential must be on established contraceptives 28 days before dosing begins.

Potential Risk of Clinical Significance	Summary of Data/Rationale for Risk	Mitigation Strategy
	
historical control data and this is also supported in literature (Posobiec, 2016)
 
No similar changes were seen in the rat after substantially higher exposure.
 
There is no data available on the effect of GSK2646264 in pregnancy and lactation in humans.
	

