## 5.1. Inclusion Criteria

A subject will be eligible for inclusion in this study only if all of the following criteria apply:

AGE
1. Between 18 and 70 years of age inclusive, at the time of signing the informed consent.
TYPE OF SUBJECT AND DIAGNOSIS INCLUDING DISEASE SEVERITY
2. Subject values for the following parameters TSH, free T4, and free T3 within the normal range. 3. Subject has confirmed diagnosis of LET (group A only), subacute or chronic CLE as determined by the investigators.  A subject with a clinical abnormality or laboratory parameter(s) which is/are not specifically listed in the inclusion or exclusion criteria, outside the reference range for the population being studied may be included: only if the investigator in consultation with the Medical Monitor if required agree and document that the finding is unlikely to introduce additional risk factors and will not interfere with the study procedures.

WEIGHT
4. Body mass index (BMI) $\geq 19\text{kg/m}^2$ (inclusive)

SEX
5. Male OR Female
Females:
a. Non-reproductive potential defined as:
• Pre-menopausal females with one of the following:
• Documented tubal ligation
• Documented hysteroscopic tubal occlusion procedure with follow-up confirmation of bilateral tubal occlusion
• Hysterectomy
• Documented Bilateral Oophorectomy
• Postmenopausal defined as 12 months of spontaneous amenorrhea. In questionable cases a blood sample with simultaneous follicle stimulating hormone (FSH) and estradiol levels consistent with menopause (refer to laboratory reference ranges for confirmatory levels). Females on hormone replacement therapy (HRT) and whose menopausal status is in doubt will be

required to use one of the highly effective contraception methods if they wish to continue their HRT during the study. Otherwise, they must discontinue HRT to allow confirmation of post-menopausal status prior to study enrolment.

b. Reproductive potential and agrees to follow one of the options listed in the Modified List of Highly Effective Methods for Avoiding Pregnancy in Females of Reproductive Potential (FRP) (see Section 12.4) from 28 days prior to the first dose of study medication and until 12 days after the last dose of study medication and completion of the follow-up visit.

The investigator is responsible for ensuring that subjects understand how to properly use these methods of contraception.

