### 5.4.1. Safety Related Stopping Criteria for an Individual Subject

A female subject will be withdrawn from the study if a positive pregnancy test is obtained during the study.

A subject may be withdrawn from the study if they present dose limiting toxicity.

Toxicity is defined as dose-limiting toxicity if it meets the following criteria:

- Occurs within 24 hours after any dose.
- and is considered by the Investigator to be possibly or probably related to treatment

- and, for AE or laboratory abnormality, is severe
- and, for tolerability,
  - is of Grade 3 or higher for “dermal response scoring (i)”, and
  - is Grade C, F, G, or H according to the “other effects scoring (ii)” (Section [5.4.2](#) below)
- and for Thyroid function – TSH to remain within the normal range at Day 14

If dose limiting toxicity is observed in an individual, the investigator or designee may use their medical judgment to stop dosing the individual subject, and is required to immediately inform the GSK medical monitor or designee. They will then decide whether it is necessary for the Safety Review Team (SRT: See Section [10.8](#)) to be convened immediately for review of the data and decision on dose adjustment or withdrawal of the individual subject.

The SRT will:

- Evaluate and confirm potential dose-limiting toxicities both as data is generated (so-called ‘in-stream review’), and at any point during the study when a bulk of data review is determined necessary (e.g. this may be conducted once all subjects in group A complete all study visits, or at any other point during study conduct).
- Pause enrolment and/or request safety-related changes to the trial protocol.

At a minimum (but not limited to), the following data-sets will be reviewed by the SRT:

- Clinical laboratory assessments
- Vital signs
- Adverse (& serious adverse) Events
- Local tolerability assessments

Additional data-sets not listed above may also be reviewed as deemed appropriate by the SRT.

A subject may be withdrawn from the study if they present a Serious Adverse Event (SAE), regardless of its severity, and reasonably attributable in the opinion of the investigator to dosing with GSK2646264.

A subject will be withdrawn if they require concomitant medications as specified and listed in Section [5.2](#).

In the presence of any of the above events, every effort will be made to take a blood sample at the time of the event for pharmacokinetics analysis.

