## 12.4. **Appendix 4: Modified List of Highly Effective Methods for Avoiding Pregnancy in Females of Reproductive Potential (FRP)**

This list does not apply to FRP with same sex partners, when this is their preferred and usual lifestyle or for subjects who are and will continue to be abstinent from penile-vaginal intercourse on a long term and persistent basis.

- Contraceptive subdermal implant
- Intrauterine device or intrauterine system
- Oral Contraceptive, with combined estrogen and progestogen [[Hatcher](#), 2011]
- Injectable progestogen [[Hatcher](#), 2011]
- Contraceptive vaginal ring [[Hatcher](#), 2011]
- Percutaneous contraceptive patches [[Hatcher](#), 2011]
- Male partner sterilization with documentation of azoospermia prior to the female subject's entry into the study, and this male is the sole partner for that subject [[Hatcher](#), 2011].
- Male condom plus partner use of one of the contraceptive options below:
  - Contraceptive subdermal implant
  - Intrauterine device or intrauterine system
  - Oral Contraceptive, either combined or progestogen alone Injectable progestogen [[Hatcher](#), 2011]
  - Contraceptive vaginal ring [[Hatcher](#), 2011]
  - Percutaneous contraceptive patches [[Hatcher](#), 2011]

This is an all inclusive list of those methods that meet the GSK definition of highly effective: having a failure rate of less than 1% per year when used consistently and, correctly and, when applicable, in accordance with the product label. For non-product methods (e.g. male sterility), the investigator determines what is consistent and correct use. The GSK definition is based on the definition provided by the ICH [[ICH, M3 \(R2\)](#) 2009].

The investigator is responsible for ensuring that subjects understand how to properly use these methods of contraception.

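### Section 4.6.1 says lactating women are not eligible, but nothing in Section 5 or the visit schedules carries this out, and pregnancy is handled only by testing and withdrawal

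*Protocol*

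**What the plan says.** Protocol Section 4.6.1 opens its risk table with pregnancy and lactation. The data column reports fetal malformations in one rabbit strain and judges them unlikely to be due to the drug, because a second strain did not show them. It then adds: "There is no data available on the effect of GSK2646264 in pregnancy and lactation in humans." The mitigation column begins with an eligibility statement: "Women who are pregnant, lactating or are planning on becoming pregnant during the study are not eligible to participate." It continues with pregnancy testing and contraception, and refers to Section 5.1 for the latter.

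Section 5 sets the criteria that sites work through, and its opening text permits no deviations from them. Section 5.1 is introduced by "A subject will be eligible for inclusion in this study only if all of the following criteria apply", and Section 5.2 frames the exclusions in the same way. For a woman of reproductive potential, inclusion 5b reads "Reproductive potential and agrees to follow one of the options listed in the Modified List of Highly Effective Methods for Avoiding Pregnancy". The commitment runs "from 28 days prior to the first dose of study medication and until 12 days after the last dose of study medication" and until the follow-up visit is complete.

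The one rule in Section 5 that acts on pregnancy itself is a withdrawal rule in Section 5.4.1: "A female subject will be withdrawn from the study if a positive pregnancy test is obtained during the study." Section 7.1 schedules pregnancy tests at Screening, on Day 1 and Day 14 (both before dosing), and at follow-up.

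**The concern.** An eligibility rule works only if it stands where eligibility is checked. Investigators screen against the numbered criteria in Sections 5.1 and 5.2, not against the risk table.

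The other drug-related rows of that table that rely on ineligibility were carried across. The thyroid row became inclusion 2 and exclusions 7 and 8, and the hypersensitivity row became exclusion 14. The pregnancy and lactation row has no matching entry exclusion, which looks like an omission and not a decision.

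The benefit-risk conclusion in Section 4.6.3 rests on the mitigations being in force. For lactation, a site following Section 5 to the letter could enrol and treat a woman whom that conclusion assumes is absent, on a question where the protocol says it has no human data. The protocol deliberately admits women of reproductive potential, so the case is not fanciful.

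**Working it through.** No figure is involved, so the check is a reading of every criterion. The inputs are Section 4.6.1, inclusions 1 to 11, exclusions 1 to 25, Sections 5.4 and 5.4.1, the schedules in Section 7.1, Section 7.4.2 and Appendix 4. Both criteria lists run unbroken in the public text, so redaction does not explain a gap.

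**Count over 11 + 25 = 36 criteria**

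- Criteria that mention lactation or breastfeeding: 0 of 11 inclusions and 0 of 25 exclusions.
- Criteria that make pregnancy or a positive pregnancy test a bar to entry: 0 of 36.
- Criteria that bar planned pregnancy in effect: 1 of 36 (inclusion 5b).

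**The three groups set side by side**

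| Group named in 4.6.1 | Entry criterion in 5.1 or 5.2 | Other control |
|---|---|---|
| Lactating | None | None in 5.4, 5.4.1 or the 7.1 schedules |
| Pregnant | None | Tests at Screening and Day 1 pre-dose; withdrawal under 5.4.1; study medication stopped under 7.4.2 |
| Planning pregnancy | 5b, in effect | A woman planning to conceive in the window cannot agree to the contraception required |

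Inclusion 5b has one possible gap. Appendix 4 says "This list does not apply to FRP with same sex partners, when this is their preferred and usual lifestyle", and it also exempts women who are abstinent on a long-term basis. For them, 5b does not clearly settle planned pregnancy.

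**Two discretionary clauses do not fill the lactation gap.** The note under inclusion 3 concerns clinical abnormalities and laboratory values outside the reference range. Exclusion 10 concerns clinically significant haematology, chemistry or urinalysis findings. Lactation is none of these.

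**Test case.** Take a breastfeeding woman who has agreed to a listed contraceptive method for the required window, has negative tests at Screening and on Day 1, and otherwise qualifies.

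1. Inclusions 1 to 11 are all met.
2. None of exclusions 1 to 25 applies.
3. Nothing in Section 5.4 or 5.4.1 withdraws her on account of lactation.
4. Section 4.6.1 says she is not eligible.

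Steps 1 to 3 and step 4 cannot both describe the intended population.

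**The case against.** **The risk table is protocol text.** Section 4.6 presents it as the mitigation strategy for this protocol. Inclusion 6 ties consent to the restrictions in the consent form and the protocol, and the consent form is not available to us. This stands: a rule exists, and the defect is an unreconciled inconsistency. It does not remove the problem, because the rule is missing from the lists against which sites determine eligibility.

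**Pregnancy is caught before dosing.** Inclusion 8 treats the study period as running from screening to follow-up, and Section 5.3 counts anyone who consents but is never randomised as a screen failure. On that reading a positive Screening or Day 1 test falls within the study and triggers withdrawal under Section 5.4.1 before any cream is applied. This stands. What is missing for pregnancy is a numbered criterion against which to record the failure.

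**Planned pregnancy is covered by inclusion 5b.** This stands, apart from the women exempted in Appendix 4.

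**The hazard is modest.** The protocol considers the rabbit findings unlikely to be drug-related, saw no similar changes in rats, and predicts exposures within its safety margins (Section 4.5). This stands as a limit on seriousness. It says little about lactation, for which the table offers only the lack of human data.

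**Conclusion.** The concern holds for lactation: Section 4.6.1 declares an ineligibility that Section 5 does not implement, and no other control compensates. For pregnancy, the gap is the lack of an entry criterion, with testing and withdrawal as a working backstop. For planned pregnancy, only the women exempted in Appendix 4 are in doubt. The number of lactating candidates is not given and is assumed to be small. This is a low-cost eligibility contradiction to be reconciled.

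A reader might infer more, but the documents do not support it:

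- *That Section 5 controls none of the three groups.* Inclusion 5b and Section 5.4.1 show otherwise.
- *That most of the sample is affected.* The cited 9:1 female-to-male ratio applied to about 20 randomised gives 20 × 0.9 = 18. That counts women, not lactating women. The ratio describes the disease and includes women who are not of reproductive potential.
- *That photoprovocation in Group A makes the matter worse.* The only ultraviolet risk in Section 4.6.1 is skin cancer, so nothing there links irradiation to lactation.
- *That such an enrolment would escape SAP Listing 7.* SAP Section 4.1 bases the inclusion/exclusion summary on an eCRF page that is not among the documents. The important-deviation outputs (Table 1.5 and Listing 6) might capture the case in any event.

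**What to change.** Reconcile Section 4.6.1 with Sections 5.1, 5.2 and 5.4.1. The direct way is to carry the sponsor's own stated eligibility rule into Section 5.2 as a numbered criterion covering all three groups, and to add the matching line to the eCRF inclusion/exclusion page. Link the pregnancy part to the Screening and Day 1 tests that already exist, so that a positive result has a criterion to be recorded against. Record lactation status at the existing Screening visit. State how the planned-pregnancy part applies to women whom Appendix 4 exempts from the contraceptive list.

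The cost is one added criterion and one eCRF line, with no new test or visit.

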#### **4.6.2. Benefit Assessment**

This study contributes to the development of medicines in an area of unmet need. Key opinion leaders and patients have highlighted the need for a new and effective topical formulation, suitable for long term use on exposed areas, with a favourable safety and tolerability profile in comparison to topical steroids and immunosuppressants. In particular, a reduction in the extent of scarring caused by lesions in exposed areas such as the face and scalp is urgently required and would greatly impact on the QoL in patients with CLE.

All patients in group B of the study will receive study drug on at least one CLE skin lesion for up to 28 days. This may improve the treated lesion and may have minor short term benefit in terms of appearance of the lesion and associated itch and pain.

#### **4.6.3. Overall Benefit: Risk Conclusion**

Taking into account the measures taken to mitigate the risk of patients taking part in this study, the associated risks are justified by the anticipated long term benefit to patients with CLE.

### **5. SELECTION OF STUDY POPULATION AND WITHDRAWAL CRITERIA**

Specific information regarding warnings, precautions, contraindications, adverse events, and other pertinent information on the GSK investigational product or other study treatment that may impact subject eligibility is provided in the Investigator Brochure [GlaxoSmithKline Document Number: [2013N182566\\_02](#), GlaxoSmithKline Document Number [2015N268236\\_01](#) (Supplement 1) and GlaxoSmithKline Document Number [2016N281634\\_00](#) (Supplement 2)]

Deviations from inclusion and exclusion criteria are not allowed because they can potentially jeopardize the scientific integrity of the study, regulatory acceptability or subject safety. Therefore, adherence to the criteria as specified in the protocol is essential. All inclusion/exclusion criteria and withdrawal criteria apply to subjects in both Part A and Part B, unless specifically stated otherwise.

## 5.1. Inclusion Criteria

A subject will be eligible for inclusion in this study only if all of the following criteria apply:

AGE
1. Between 18 and 70 years of age inclusive, at the time of signing the informed consent.
TYPE OF SUBJECT AND DIAGNOSIS INCLUDING DISEASE SEVERITY
2. Subject values for the following parameters TSH, free T4, and free T3 within the normal range. 3. Subject has confirmed diagnosis of LET (group A only), subacute or chronic CLE as determined by the investigators.  A subject with a clinical abnormality or laboratory parameter(s) which is/are not specifically listed in the inclusion or exclusion criteria, outside the reference range for the population being studied may be included: only if the investigator in consultation with the Medical Monitor if required agree and document that the finding is unlikely to introduce additional risk factors and will not interfere with the study procedures.

WEIGHT
4. Body mass index (BMI) $\geq 19\text{kg/m}^2$ (inclusive)

SEX
5. Male OR Female
Females:
a. Non-reproductive potential defined as:
• Pre-menopausal females with one of the following:
• Documented tubal ligation
• Documented hysteroscopic tubal occlusion procedure with follow-up confirmation of bilateral tubal occlusion
• Hysterectomy
• Documented Bilateral Oophorectomy
• Postmenopausal defined as 12 months of spontaneous amenorrhea. In questionable cases a blood sample with simultaneous follicle stimulating hormone (FSH) and estradiol levels consistent with menopause (refer to laboratory reference ranges for confirmatory levels). Females on hormone replacement therapy (HRT) and whose menopausal status is in doubt will be

required to use one of the highly effective contraception methods if they wish to continue their HRT during the study. Otherwise, they must discontinue HRT to allow confirmation of post-menopausal status prior to study enrolment.

b. Reproductive potential and agrees to follow one of the options listed in the Modified List of Highly Effective Methods for Avoiding Pregnancy in Females of Reproductive Potential (FRP) (see Section 12.4) from 28 days prior to the first dose of study medication and until 12 days after the last dose of study medication and completion of the follow-up visit.

The investigator is responsible for ensuring that subjects understand how to properly use these methods of contraception.

## INFORMED CONSENT

6. Capable of giving signed informed consent as described in Section 10.2 which includes compliance with the requirements and restrictions listed in the consent form and in this protocol.

## RELEVANT HABITS

7. All subjects must be free from scarring or skin markings (e.g. tattoos or piercings) and open wounds on the defined areas of the body that cream will be applied onto or that will be exposed to PV, unless in the opinion of the investigator it will not compromise the subjects' safety and quality of data.

8. Able to refrain from exposure to extended and direct sunlight during the study period, from screening until follow up, especially the area that is under treatment during the study.

9. Able to refrain from using self-tanning products on the areas on which the study cream will be applied for the duration of the study from screening to follow-up.

10. Able to refrain from shaving and waxing the areas on which the study cream will be applied during the duration of the study from screening to follow up.

## PERMITTED MEDICATIONS

11. Patient stable on either no treatment or on :

- **Corticosteroids** ( $\leq 7.5$ mg/day prednisone or prednisone equivalent or less) for a minimum of 30 days prior to screening and through to Day 28.
- and /or **hydroxychloroquine** ( $\leq 400$ mg daily dose) for a minimum of 60 days prior to the initial photoprovocation for group A or Randomisation Visit for group B through to day 28.
- **Topical steroids** applied to the defined areas of the body that are not exposed to photoprovocation or study cream from screening to Day 28.
- **Topical calcineurin inhibitors and retinoids** applied to the defined areas of the body that are not exposed to photoprovocation or study cream from screening to Day 28.
- **Opioids, if required for acute and chronic pain management, and documented in the medical history/records**

## 5.2. Exclusion Criteria

A subject will not be eligible for inclusion in this study if any of the following criteria apply:

CONCURRENT CONDITIONS/MEDICAL HISTORY (INCLUDES LIVER FUNCTION AND QTC INTERVAL)

1. ALT >2xULN;
 
2. Bilirubin >1.5xULN (isolated bilirubin >1.5xULN is acceptable if bilirubin is fractionated and direct bilirubin <35%)
 
3. Current or chronic history of liver disease, or known hepatic or biliary abnormalities (with the exception of Gilbert's syndrome or asymptomatic gallstones)
 
4. QTcF > 450 msec, or QTcF > 480 msec in subjects with Bundle Branch Block
 
NOTES:
 
 
• The QTc is the QT interval corrected for heart rate according to Bazett's formula (QTcB), Fridericia's formula (QTcF), and/or another method, machine-read or manually over-read.
 
• The specific formula that will be used to determine eligibility and discontinuation for an individual subject should be determined prior to initiation of the study. In other words, several different formulae cannot be used to calculate the QTc for an individual subject and then the lowest QTc value used to include or discontinue the subject from the trial.
 
• For purposes of data analysis, QTcB, QTcF, another QT correction formula, or a composite of available values of QTc will be used as specified in the Reporting and Analysis Plan (RAP).
 
 
5. History of any past or present benign or malignant skin conditions and disease, unless in the opinion of the investigator it will not compromise the subjects safety and quality of data.
 
6. Subjects with active Systemic Lupus Erythematosus (SLE) and/or significant disease in any other organ than the skin, as judged by the Investigator after discussion with the medical monitor
 
7. Subjects with a history of Graves disease
 
8. Subjects with a history of thyroid cancer.
 
9. Unable to refrain from vitamins, herbal and dietary supplements (including St John's Wort) within 7 days (or 14 days if the drug is a potential enzyme inducer) or 5 half lives (whichever is longer) prior to the screening visit until the completion of the follow-up assessments, unless in the opinion of the Investigator, in consultation with the GSK Medical Monitor if required, the medication will not interfere with the study procedures or compromise subject safety.
 
10. Clinically significant abnormality in the hematological, clinical chemistry, or urinalysis screen, that in the opinion of the investigator after discussion with the


medical monitor, requires further investigation, medical intervention or poses a safety risk to the subject to participate in the trial.

11. Subjects who start prohibited medications or therapies at any time during the study will be withdrawn from the study.

The following medications and therapies are prohibited at any time during the study:

- Use of other investigational agents (biologic or non-biologic; investigational applies to any drug not approved for sale in the country in which it is used).
- Co-enrolment into another study of an investigational agent or non-drug therapy.
- Use of biological agents (e.g., alemtuzumab, rituximab, ATG) during the clinical study or within 12 months to first dose of study treatment.
- Use of other immunosuppressive drugs commonly used in SLE including Azathioprine, Methotrexate, Mycophenolate, Cyclophosphamide within 3 months to first dose of study treatment.

